1.0 TRIAL SUMMARY

1.1 Objectives

1.1.1 Primary objective:

1.) To assess physician-reported acute grade 3 or greater gastrointestinal, genitourinary and hematologic toxicities at 12 weeks post-treatment for patients treated with linear energy transfer (LET)-optimized, intensity-modulated proton therapy (IMPT) and compare to contemporary controls treated with VMAT to determine the feasibility of this outcome for a future randomized trial.

1.1.2 Secondary objectives:

1.) To assess the feasibility of enrolling patients on a prospective trial delivering LET-optimized IMPT for newly diagnosed, non-metastatic anal cancer.
2.) To develop guidelines and workflow to create and deliver anal canal cancer treatments using LET-optimized IMPT.
3.) To evaluate complete response rate at 12 weeks and 24 weeks post-treatment.
4.) To evaluate local progression free survival, distant metastasis-free survival and overall survival at 24 and 48 months.
5.) To evaluate rates of patient-reported acute toxicity, function, distress and QOL at 12 weeks.
6.) To evaluate rates of patient-reported late toxicity, function, distress and QOL every 6 months for 24 months.
7.) To evaluate the value of proton therapy by comparing Time-Driven Activity-Based Costing data from the date of consultation until the date of the 12-week follow up visit post-treatment with contemporary controls treated with VMAT.

1.1.3 Exploratory objectives:

1.) To compare dose to the pelvic bone marrow, bowel, bladder and genitalia between LET-optimized IMPT, traditionally-optimized IMPT and VMAT.
2.) To assess rates of leukopenia, neutropenia and lymphopenia at 12-weeks post-treatment for patients treated with LET-optimized IMPT and compare to contemporary controls treated with VMAT.
3.) To correlate white blood cell counts (WBC), absolute neutrophil counts (ANC) and absolute lymphocyte counts (ALC) with dose to the pelvic bone marrow for patients treated with LET-optimized IMPT.

Abbreviated Title	IMPT for Anal Cancer
Trial Phase	Feasibility
Clinical Indication	Newly diagnosed, non-metastatic squamous cell carcinoma of the anal canal dispositioned to definitive chemoradiation treatment
Trial Type	Treatment
Type of control	None
Route of administration	External beam proton radiation therapy with concurrent chemotherapy
Trial Blinding	NA
Treatment Groups	Single arm, non-randomized
Number of trial subjects	40
Estimated duration of trial	9 years
Duration of Participation	9 years

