- 6.3.8 Patients should be followed every 12+/-4 weeks for the first two years per the current standard of care with physical exam, labs, imaging and endoscopy at the discretion of the treating physicians (See Table 2). Only the first follow-up visit will be required on study. However, the questionnaires mentioned in 6.3.7 above will be sent via email using REDCap at 6 month intervals for voluntary participation for 24 months after treatment completion. Patients returning for follow up at MD Anderson will have their medical records queried for response rate, local progression free survival, distant metastasis-free survival and overall survival at each subsequent visit for 48 months after treatment completion.

Table 2

Time from Completion of Treatment	Evaluation	Team Providing Clinical Follow-up
3 months	PE, CT, scope	MO, XRT, CRS
6 months	PE, scope	MO + CRS*
9 months	PE	XRT
12 months	PE, CT, scope	MO + CRS
15 months	PE	XRT
18 months	PE, CT (CT not needed if <T3 or <N2)	MO
21 months	PE	XRT
24 months	PE, CT, scope	MO + CRS
30 months	PE	XRT
36 months	PE, CT, scope	MO
42 months	PE	XRT
48 months	PE, CT	MO
>48 months		Survivorship or discharge to PCP for routine care

*initial visits with CRS for proctoscopy until complete response or disease persistence is established.

PE = physical exam, CT = computed tomography, MO = medical oncology, XRT = radiation oncology, CRS = colorectal surgery, PCP = primary care physician.

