7.1 Data Collection, Management and Statistical Summary

Study data will be collected and managed using REDCap (Research Electronic Data Capture) electronic data capture tools hosted at MD Anderson ²⁷. REDCap (<http://www.project-redcap.org>) is a secure, web-based application with controlled access designed to support data capture for research studies, providing: 1) an intuitive interface for validated data entry; 2) audit trails for tracking data manipulation and export procedures; 3) automated export procedures for seamless downloads to common statistical packages; and 4) procedures for importing data from external sources. In the case of multi-center studies REDCap uses Data Access Groups (DAGs) to ensure that personnel at each institution are blinded to the data from other institutions. REDCap (<https://redcap.mdanderson.org>) is hosted on a secure server by MD Anderson Cancer Center's Department of Research Information Systems & Technology Services. REDCap has undergone a Governance Risk & Compliance Assessment (05/14/14) by MD Anderson's Information Security Office and found to be compliant with HIPAA, Texas Administrative Codes 202-203, University of Texas Policy 165, federal regulations outlined in 21CFR Part 11, and UTMDACC Institutional Policy #ADM0335. Those having access to the data file include the study PI and research team personnel. All protected health information (PHI) will be removed from the data when it is exported from REDCap for analysis. All dates for a given patient will be shifted by a randomly generated number between 0 and 364, thus preserving the distance between dates. Dates for each

patient will be shifted by a different randomly generated number. Following publication study data will be archived in REDCap.

General descriptive statistics will be computed to report toxicity and outcome metrics. In addition, descriptive statistics will describe pretreatment patient demographics including age, gender, and performance status as well as disease-related characteristics including disease tumor and nodal stage. All time to event analyses will start from the time of enrollment.

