- Secondary Endpoint #4: *To evaluate local progression-free survival, distant metastasis-free survival and overall survival at 24 and 48 months.*
 - Patients will follow up with their treating physician at every 3-6 months per the current standard of care MD Anderson gastrointestinal center follow-up algorithm (Table 2).
 - Local Failure/Progression: Either recurrence of disease in the anal canal following clearance, progression of disease in the anal canal after completion of treatment or persistence of disease in the anal canal for more than 6 months after completion of treatment.
 - Distant Metastatic Failure: the appearance of distant metastatic disease.
 - Disease-Free Survival: measured as time to locoregional failure, appearance of distant metastases or death due to any cause.
 - Overall Survival: measured as time due to death due to any cause.
 - We will estimate LPFS, DMFS, and OS from time of enrollment using the Kaplan-Meier method and report estimates with appropriate 95% confidence intervals.
 - For local and regional failure, the date of failure will be recorded as 6 months after the completion of treatment in the case of persistent, biopsy-proven disease after 6 months status-post completion of all therapy.
- Secondary Endpoint #5: *To evaluate rates of patient-reported acute toxicity, function, distress and QOL at 12 weeks post-treatment.*

- PRO-CTCAE will be collected weekly during treatment and also at the 12 week post-treatment follow up visit
- EQ-5D will be collected at baseline and also at the 12 week post-treatment follow-up visit
- The EORTC QLQ- C30will be collected at baseline and also at the 12 week post-treatment followup visit
- Treatment-Related Stress Questionnaire and the Perceived Stress Scale will be collected at baseline and also at the 12 week post-treatment followup visit
- For female patients:
 - Female Sexual Function Index (FSFI)- 19 question survey validated in cancer survivors will be collected at baseline and also at the 12 week post-treatment followup visit.
- For male patients:
 - International Index of Erectile Function Questionnaire (IIEF) will be collected at baseline and also at the 12 week post-treatment followup visit

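### LPFS and DMFS are read 24 and 48 months after enrollment, but the 24- and 48-month examinations are counted from the end of treatment, so both estimates err upward

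*Combined protocol and SAP*

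**What the plan says.** Section 7.1 sets a general rule: "All time to event analyses will start from the time of enrollment". Section 7.4.2 repeats it for this endpoint: "We will estimate LPFS, DMFS, and OS from time of enrollment using the Kaplan-Meier method". The objective there is "To evaluate local progression-free survival, distant metastasis-free survival and overall survival at 24 and 48 months", and section 1.1.2 gives the same two time points.

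For the examinations behind these endpoints, section 7.4.2 has patients followed every 3 to 6 months "per the current standard of care MD Anderson gastrointestinal center follow-up algorithm (Table 2"). The first column of Table 2 is headed "Time from Completion of Treatment". On that clock the table places:

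- physical exam, CT and scope at 12, 24 and 36 months;
- physical exam and CT at 18 months, with the note "CT not needed if <T3 or <N2";
- physical exam alone at 15, 21 and 42 months;
- physical exam and CT at 48 months.

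Section 6.3.8 also counts from the end of treatment: records of patients who return are queried for 48 months after completion. The only rule for dating a failure, in section 7.4.2, concerns persistent disease, which is dated 6 months after completion. Nothing links the two clocks.

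**The concern.** The 24- and 48-month read-outs carry the same labels as two Table 2 visits, so a reader would expect the curves to include what those visits find. The labels belong to different clocks. The 24-month visit is the first since month 12 for which Table 2 lists physical exam, CT and scope together, and on Table 2's nominal timing it comes after the 24-month read-out. The 48-month CT likewise comes after its own.

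Scheduled testing can find a failure late but not early, so the error runs one way: LPFS and DMFS look better than they are. The section 2.2 hypothesis includes similar or superior tumor response, and these curves are the trial's longer-term evidence on tumor control.

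**Working it through.** The plan states no expected LPFS or DMFS, so there is no figure to reproduce. The check has two parts: timing, which follows from the documents, and size, which needs assumed failure rates.

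**Inputs for timing**

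- Enrollment to start of chemoradiation: 0 to 30 days (section 6.1.1; enrollment is taken to fall in this screening period).
- Course length: 25 to 29 fractions (section 5.1.5). With a Monday start, five fractions a week and no breaks (assumed), this is 32 to 38 days from first to last fraction.
- Enrollment to completion: 0 + 32 = 32 days to 30 + 38 = 68 days. Divided by 30.4375, that is 1.05 to 2.23 months.
- Visit window: plus or minus 4 weeks, stated in section 6.3.8 for the first two years only.

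**Timing.** Months from enrollment = Table 2 month + offset.

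| Table 2 visit | Tests | Months from enrollment |
|---|---|---|
| 12 | PE, CT, scope | 13.1 to 14.2 |
| 18 | PE, CT unless waived | 19.1 to 20.2 |
| 21 | PE | 22.1 to 23.2 |
| **24** | **PE, CT, scope** | **25.1 to 26.2** |
| 36 | PE, CT, scope | 37.1 to 38.2 |
| 42 | PE | 43.1 to 44.2 |
| **48** | **PE, CT** | **49.1 to 50.2** |

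With the window, the earliest 24-month visit is 24 + (32 − 28)/30.4375 = 24.13 months and the latest is 24 + (68 + 28)/30.4375 = 27.15 months. Treatment breaks push both later.

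**Size for DMFS.** Assume a constant hazard, an offset of 1.9 months, metastases found only at scheduled CT, and failures dated when found. If true cumulative failure at read-out T is F, then λ = −ln(1 − F)/T, and the curve at T shows 1 − exp(−λ × time of last CT).

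- T = 24, 18-month CT waived, last CT at 12 + 1.9 = 13.9 months. True 10/15/20% shows as 5.9/9.0/12.1%. Overstatement: 4.1/6.0/7.9 points.
- T = 24, 18-month CT done, last CT at 19.9 months. True 10/15/20% shows as 8.4/12.6/16.9%. Overstatement: 1.6/2.4/3.1 points.
- T = 48, last CT at 36 + 1.9 = 37.9 months. True 15/20/25% shows as 12.0/16.2/20.3%. Overstatement: 3.0/3.8/4.7 points.

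**Sensitivity.** If half of metastases surface between scans, the first line halves to about 2 to 4 points. Now let the offset run from about 1.1 to 2.2 months and the hazard be either constant or front-loaded (Weibull, shape 0.6), with 10 to 20% failure at 24 months. The 24-month overstatement is then 2.6 to 8.6 points where the last CT or scope was at 12 months, and 0.9 to 3.8 where the last CT was at 18. For failures that the 21-month physical exam would detect it is 0.2 to 1.5 points.

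**Scale.** With 40 patients and complete follow-up, the 95% half-width is 1.96 × √(S(1 − S)/40): 9.3 points at S = 0.90 and 12.4 at S = 0.80. Four to eight points is 1.6 to 3.2 patients in 40.

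**The case against.** Several points on the other side stand.

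- A reader might infer that the 24-month visit can never fall inside the read-out. That holds only on Table 2's nominal month, and at the extreme by 4 days. Section 6.3.8 also describes follow-up every 12 weeks, give or take 4. An eighth visit at 96 weeks (672 days) would fall 704 to 740 days, or 23.1 to 24.3 months, after enrollment. Only the first follow-up visit is mandatory on study. Table 2 nevertheless places the CT and scope at 24 months.
- Later endoscopy depends on findings (section 6, Table 1, note e), and section 6.3.8 leaves exams, imaging and endoscopy to physician discretion. Such tests, symptoms and the exams at 15, 18 and 21 months bring failures forward, most of all in the anal canal. The bias is therefore smaller for LPFS.
- The 4 to 8 points apply only where the 18-month CT is waived and nothing surfaces between scans. Read literally, the note waives that CT for anyone below either threshold, but the documents give no stage mix, so the share affected is unknown.
- Much of the shortfall reflects the spacing of CTs; the offset itself is only 1 to 2 months. It matters because it moves the next CT and scope past the read-out.
- A reader might infer that the error favors IMPT over VMAT. No LPFS or DMFS comparison is planned; only the absolute estimates are affected. Nor are failures lost: they appear on the same curve a month or two later.
- No window is stated for month 48, and the record query already runs past a 48-month read-out from enrollment. The query matters only for capturing the 48-month visit itself.

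These points limit the size of the problem. None of them aligns the two clocks.

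**Conclusion.** The mismatch is real and its direction is upward. Followed on Table 2's nominal timing, the 24-month physical exam, CT and scope and the 48-month physical exam and CT all come after the read-outs that share their labels.

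Under a constant hazard and detection only at scheduled CT, DMFS at 24 months is overstated by about 1.6 to 3.1 points with the 18-month CT and 4 to 8 without it, for assumed failure of 10 to 20%. At 48 months it is overstated by about 3 to 5 points for assumed failure of 15 to 25%. These sizes are illustrative because the plan states no rates. They also assume that failures are dated when found, which is usual but is not stated. LPFS is affected in the same direction, probably less.

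Persistent disease is unaffected, since its assigned date falls about 7 to 8 months after enrollment, and so is OS. The endpoint is secondary and descriptive, and the bias is smaller than the sampling error at 40 patients. The confidence interval does not cover a systematic error, however, and the correction is cheap, so it should be made.

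**What to change.** Keep enrollment as the origin and leave the visit schedule as it is. In section 7.4.2:

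1. Beside the 24- and 48-month values, report LPFS and DMFS at a time after those visits have closed, labelled with that time. About month 27 to 28 suits the first (latest visit 27.15 months without breaks). About month 51 to 52 suits the second if a 4-week window is assumed: 48 + (68 + 28)/30.4375 = 51.15.
2. Add an interval-censored estimate at 24 and 48 months as a sensitivity analysis.
3. State that failures other than persistent disease are dated when found.

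In section 6.3.8, extend the record query until the 48-month visit has taken place.

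The labels matter because a later read-out includes failures that arose after 24 months. On the constant-hazard assumption, failure by 25.9 months is 10.7% or 21.4% when the 24-month value is 10% or 20%, so 0.7 to 1.4 points more. For the same reason, do not back-date events to nominal visit months. Moving the origin to completion of treatment is not advised either. It would put DMFS and OS on different clocks, need an imputed origin for patients who do not complete treatment, and still miss visits late in the window.

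The cost is some SAP wording, a little more analysis and follow-up, and slightly less favorable LPFS and DMFS figures.

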5.1.2 IMPT Planning and Plan Evaluation

The following is the series of steps in the IMPT planning process for each patient:

1. An MFO-IMPT plan will be designed using a commercial (clinical) treatment planning system (TPS) based on the current practice of using criteria defined in terms of dose- and dose-volume constraints and RBE = 1.1. (The Fixed RBE-IMPT plan.)
2. For the LET-optimized IMPT plan, dose distribution will be optimized using dose- and dose-volume criteria extended to include terms that increase LET in the target and reduce it in normal tissues. Such planning will require the use of an in-house TPS based on Monte Carlo techniques. Post-processing of scanning spots to ensure deliverability will also be performed as is done in the clinical TPS.
3. Both 1) IMPT and 2) LET-optimized IMPT will be reported in terms of three distributions: a) fixed RBE weighted dose (RBE=1.1), b) dose-averaged LET, and c) variable RBE-weighted dose (employing the RBE model of McNamara et al 2015) computed using Monte Carlo simulations. These distributions, dose- and LET-volume histograms and indices derived therefrom will be compared and presented to physicians to support decision making.
4. For safety considerations and for consistency with traditional practice, all dose distributions expressed in terms of RBE of 1.1 will be used to make final treatment decisions. To accomplish this, LET-optimized IMPT plan will be imported back into the current clinical TPS, Plan 1) and 2) will be renormalized to require the same target coverage and compared.
5. The dose distribution that best meets the dose requirements in the RBE=1.1 domain (Step 4) and maximizes the target LET while minimizes LET to critical structures (Step 3), as judged by the attending physician, will be chosen for treatment. If LET-optimized IMPT plan is not deemed significantly superior, the conventional IMPT plan will be chosen.
6. The selected plan will be approved in the clinical TPS and processed for quality assurance and treatment delivery.

5.1.3 GTV and CTV should be delineated on each axial slice of the planning CT scan on which they appear.

- GTVp includes the gross primary tumor in the anal canal as documented by physical exam, endoscopic exam, CT, PET and MRI.
- GTVn includes all involved nodes as documented by imaging or biopsy.
- CTVp includes the GTVp with a 1 cm margin except into uninvolved bone.

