6.5 Correlative Analyses

6.5.1 Both traditionally-optimized IMPT and LET-optimized IMPT plans will be generated for each patient enrolled on study. The goal of LET-optimized IMPT is to maximize the LET within the target and minimize it in normal tissues while maintaining the coverage requirements for target volumes and dose volume constraints for OARs expressed in terms of (RBE=1.1) weighted doses. This requirement is imposed to assure safety and for consistency with the current practice. The difference in dose distribution between IMPT and LET-optimized IMPT plans is expected to be minimal to moderate. Even though constraints are fully met, due to possible redistribution of high LET values from normal tissues into target volumes in LET-optimized IMPT plans, for some cases mean dose to surrounding critical organs may be increased. Our goal is to evaluate the safety of such differences in dose distributions.

6.5.2 Blood will be drawn at baseline, weekly during chemoradiation and at the 12-week post-treatment follow up visit as per standard of care (Table 1). WBC, ANC and ALC values will be recorded from the standard of care CBC drawn and their nadirs will be correlated with radiation dose to the pelvic bone marrow.

7.0 STASTICAL PLAN:

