7.4 Statistical Analysis Plan

7.4.1 Primary Clinical Endpoint: *To assess physician-reported acute grade 3 or greater gastrointestinal, genitourinary and hematologic toxicities at 12 weeks post-treatment for patients treated with linear energy transfer (LET)-optimized, intensity-modulated proton therapy (IMPT) and compare to contemporary controls treated with VMAT to determine the feasibility of this outcome for a future randomized trial.*

- At baseline, weekly during treatment, and at the 12 week post-treatment follow up appointment, the treating physician will document physician-assessed acute hematologic, gastrointestinal, genitourinary, dermatologic and other toxicities according to the Common Toxicity Criteria for Adverse Events v-4 (CTCAE v4).
- For each cumulative physician-reported toxicity (hematologic, gastrointestinal, genitourinary, dermatologic and other) at 12-weeks post-treatment, we will tabulate results by type, grade, and attribution and compare with contemporary controls treated with standard of care VMAT-based chemoradiation with 5FU and cisplatin for non-metastatic anal squamous cell carcinoma manually and individually matched for (in order): T-stage, radiation dose, age and gender. We will compare toxicity rates using a McNemar's chi-squared test for paired proportions.
- A separate PA protocol will be submitted to retrospectively review the data from these contemporary controls.
- Subset analyses will be carried out to evaluate the effect of other variables that may also impact toxicity in addition to radiation modality (IMPT vs VMAT).

On RTOG 0529, patients treated with dose-painted IMRT-based concurrent CRT for anal cancer had reported worst overall G3 or greater toxicity rates of 83%. GU/GI G3 or greater toxicity rates were 21%, dermatologic G3 or greater toxicity rates were 23% and hematologic G3 or greater toxicity rates were 58% ⁴.

To ensure an LET-optimized IMPT-based CRT approach is not overly toxic, we will monitor physician-assessed toxicity using the Bayesian optimal phase 2 (BOP2) design ²⁸. Specifically, let n denote the interim sample size and N denote the maximum sample size. Let p_{tox} denote the probability of G4 or greater toxicity and define the null hypothesis $H_0: p_{tox} > 0.5$, representing that the treatment is too toxic. We will stop enrolling patients and inspect the safety data for possible trial termination if

$$Pr(p_{tox} \leq 0.5 | data) < \lambda \left(\frac{n}{N}\right)^\alpha,$$

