where λ and α are design parameters optimized to minimize the chance of incorrectly claiming that a safe treatment is unacceptable under the alternative hypothesis $H_1: p_{tox} = 0.3$, while controlling the type I error rate at 0.1 (i.e., the chance of incorrectly claiming that an overly toxic treatment is acceptable is no more than 10%). Assuming a Beta (0.5,0.5) prior distribution for p_{tox} , the above decision rule corresponds to the following stopping boundaries:

Table 3: Optimized stopping boundaries

# patients treated	Stop if # toxicity >=
10	7
20	11
30	14
40	16

Based on Table 3, we perform the interim analysis when the number of enrolled patients reaches 10, 20, 30. When the total number of patients reaches the maximum sample size of 40, we reject the null hypothesis and conclude that the treatment is acceptable if the number of toxicities are less than 16; otherwise we conclude that the treatment is unacceptable. We anticipate we will have to enroll 48 patients to have 40 evaluable patients for this analysis.

Below in Table 4 are the operating characteristics for the safety monitoring based on 10000 simulations using the BOP2 web application, which is available at <http://www.trialdesign.org>.

Table 4: Operating characteristics

Toxicity rate	Early stopping (%)	Claim acceptable (%)	Sample size
0.5	72.70	7.31	26.7

0.4	30.55	42.83	34.9
0.3	4.93	87.57	39.1
0.2	0.17	99.57	40.0
0.1	0.00	100.00	40.0

7.4.2 Secondary Clinical Endpoints:

- Secondary Endpoint #1: *To assess the feasibility of enrolling patients on a prospective trial delivering LET-optimized IMPT for newly diagnosed, non-metastatic anal cancer.*
 - We will assess accrual at 24 months after the study open to determine feasibility of enrolling 40 patients and obtaining insurance approval for IMPT treatment over the planned 9 years.
- Secondary Endpoint #2: *To develop guidelines and workflow to create and deliver anal canal cancer treatments using LET-optimized IMPT.*
 - We will present the results of our workflows in a descriptive manner.
- Secondary Endpoint #3: *To evaluate complete response rate at 12 weeks and 24 weeks post-treatment.*
 - Complete response will be defined as no evidence of disease by physical exam, endoscopy and cross-sectional imaging.
 - Complete response will be reported at 12 and 24 weeks post-treatment as determined clinically by physical exam, endoscopic examination and imaging.

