- For patient-reported acute toxicity, function, distress and QOL instruments, we will graph and summarize the distributions of scores for each instrument over time noting how many patients have data at each time point. We will analyze the changes over time using mixed effects linear models.

- Secondary Endpoint #6: *To evaluate rates of patient-reported late toxicity, function, distress and QOL every 6 months for 24 months.*
 - PRO-CTCAE, EQ-5D, EORTC QLQ-C30, treatment-related stress questionnaire, perceived stress scale, female sexual function index, and international index of erectile function questionnaire will be collected every 6 months following treatment until 24 months post-treatment.
 - For patient-reported acute toxicity, function, distress and QOL instruments, we will graph and summarize the distributions of scores for each instrument over time noting how many patients have data at each time point. We will analyze the changes over time using mixed effects linear models.

- Secondary Endpoint #7: *To evaluate the value of proton therapy by comparing Time-Driven Activity-Based Costing data from the date of consultation until the date of the 12-week follow up visit post-treatment with contemporary controls treated with VMAT.*
 - TDABC data will be collected for the entire acute episode of care from the date of consultation until the 12-week follow up post-treatment for all patients using previously generated departmental process maps. Costs will be tabulated as either treatment or toxicity-management related.

We will then compare these TDABC data with contemporary controls treated with VMAT (as described above) treated during the same fiscal year.

7.4.3 Exploratory Endpoints:

- Exploratory Endpoint #1: *To compare dose to the pelvic bone marrow, bowel, bladder and genitalia between LET-optimized IMPT, traditionally optimized IMPT and VMAT.*
 - Dosimetric studies will be performed comparing the doses from plans generated using the techniques described above.

- We will record dosimetric differences between conventionally optimized (RBE = 1.1) IMPT plans and LET-optimized IMPT plans for analysis using the Wilcoxon rank-sum test. We will also record how often the LET-optimized IMPT plan is chosen by the treating physician over the conventionally optimized (RBE = 1.1) IMPT plan.

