- Exploratory Endpoint #2: *To assess rates of leukopenia, neutropenia and lymphopenia at 12-weeks post-treatment for patients treated with LET-optimized IMPT and compare to contemporary controls treated with VMAT.*
 - We will compare the on-treatment blood count nadirs for patients treated with LET-optimized IMPT with matched historical controls treated with VMAT (as described above). Continuous variables will be compared using a Wilcoxon-Rank-Sum test and corresponding p-values will be reported.
- Exploratory Endpoint #3: *To correlate white blood cell counts (WBC), absolute neutrophil counts (ANC) and absolute lymphocyte counts (ALC) with dose to the pelvic bone marrow for patients treated with LET-optimized IMPT.*
 - For each patient treated with LET-optimized IMPT, mean bone marrow dose and bone marrow V10 will be correlated with WBC, ANC and ALC nadir using the Spearman rank correlation coefficient to evaluate for correlation.
- Exploratory Endpoint #4: *To encourage optional co-enrollment on study 2014-0543 so that tumor DNA, rectal microbiome and MRI imaging-based biomarkers can be assessed for patients receiving LET-optimized IMPT and compared with other patients enrolled on 2014-0543 receiving VMAT-based radiation.*
 - Data from tumor swabs, tumor brushings and rectal swabs will be evaluated on 2014-0543 to identify mutations in cancer related genes enriched during the course of chemoradiation. Changes in tumor gene mutations are also correlated with protein phosphorylation status. Additionally, shifts in the microbiome occurring during the course of chemoradiation in the rectal flora.
 - Data from patients coenrolled on 2014-0543 receiving LET-optimized IMPT will be compared with patients enrolled on 2014-0543 only who receive VMAT-based chemoradiation.
 - We will use descriptive statistics and graphical methods illustrate genomic mutations and rectal flora from baseline at each assessment during chemoradiation (week 1, 3 and 5).

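### Exploratory Endpoints 1 and 2 apply the unpaired Wilcoxon rank-sum test to paired data

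*Combined protocol and SAP*

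**What the plan says.** **Exploratory Endpoint 1 (7.4.3).** Differences between the conventionally optimized and "LET-optimized IMPT plans for analysis using the Wilcoxon rank-sum test" are to be recorded. The data structure is set elsewhere. Section 6.5.1 states: "Both traditionally-optimized IMPT and LET-optimized IMPT plans will be generated for each patient enrolled on study". Section 5.1.2 builds the two plans for each patient, renormalizes them to the same target coverage and compares them.

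**Exploratory Endpoint 2 (7.4.3).** On-treatment blood-count nadirs are compared with matched VMAT controls, with a reference back to the earlier description: "Continuous variables will be compared using a Wilcoxon-Rank-Sum test and corresponding p-values will be reported". That earlier description, in 7.4.1, has the controls "manually and individually matched for (in order): T-stage, radiation dose, age and gender", and tests toxicity rates with McNemar's "chi-squared test for paired proportions".

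The plan names no paired test for either continuous comparison.

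**The concern.** The rank-sum test treats its two samples as independent. In Endpoint 1 the samples are two plans on one patient's anatomy, with the same targets and equalized coverage. In Endpoint 2 they are the pairs that 7.4.1 already treats as pairs, so the plan handles one matched set in two incompatible ways.

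With positive within-pair correlation the test overstates the variance of the difference, so it rejects too rarely. Endpoint 1 bears on research question 2.1.2, whether LET optimization lowers dose to marrow, bladder, bowel and genitalia. Section 6.5.1 expects only small to moderate plan differences, which is where lost power matters most. It also warns that "for some cases mean dose to surrounding critical organs may be increased" and sets out to judge whether such differences are safe. For that purpose a conservative test is not a harmless error, because a real increase in organ dose could be reported as non-significant.

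**Working it through.** **Inputs from the documents.** There are 40 evaluable patients (7.2). Section 7.4.1 adds: "We anticipate we will have to enroll 48 patients to have 40 evaluable patients for this analysis". Since both plans are made for every enrolled patient, Endpoint 1 could have up to 48 pairs. Endpoint 2 has at most one pair per evaluable patient if matching is 1:1, which McNemar's test implies but the plan does not state.

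**Inputs assumed.** The documents give no alpha, effect size, power or within-pair correlation for these endpoints, so there is no planned figure to reproduce. I assume two-sided 5%, bivariate normal pairs with equal SDs, correlation rho, and a shift d in SD units.

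**Step 1: why the test is miscalibrated.** For n pairs, the variance of the mean difference is 2σ²(1 − rho)/n, whereas an independent-samples test uses 2σ²/n. For the rank-sum test the large-sample type I error is 2[1 − Φ(1.96/√(1 − rho_s))], with Spearman correlation rho_s = (6/π)·arcsin(rho/2).

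- rho 0.3: rho_s = 0.288, so 1.96/√0.712 = 2.32 and the type I error is 2.0%.
- rho 0.5: rho_s = 0.483, so 1.96/√0.517 = 2.73 and the type I error is 0.6%.

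Simulation with 40 pairs (10,000 replicates per setting; normal-approximation tests with continuity correction) agrees: 3.8%, 2.9%, 1.9% and 0.6% at rho 0.1, 0.2, 0.3 and 0.5, and below 0.1% at 0.7 or higher. The signed-rank test stays between 4.5% and 5.0%.

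**Step 2: power for Endpoint 1, d = 0.3 (rank-sum vs signed-rank).**

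| rho | 40 patients | 48 patients |
|---|---|---|
| 0 | 25% vs 24% | not run |
| 0.5 | 18% vs 43% | not run |
| 0.7 | 13% vs 64% | 19% vs 74% |
| 0.8 | 10% vs 81% | 15% vs 88% |
| 0.9 | 6% vs 98% | 10% vs 99% |

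These cases do not assume that every patient moves the same way. The share moving in the opposite direction is Φ(−0.3/√(2(1 − rho))): 38%, 35%, 32% and 25% at rho 0.5, 0.7, 0.8 and 0.9.

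**Step 3: power for Endpoint 2, d = 0.5 (rank-sum vs signed-rank).**

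| rho | 40 pairs | 30 pairs | 20 pairs |
|---|---|---|---|
| 0.1 | 57% vs 61% | 46% vs 49% | 31% vs 33% |
| 0.2 | 58% vs 67% | 45% vs 53% | 31% vs 37% |
| 0.3 | 59% vs 72% | 45% vs 58% | 29% vs 41% |
| 0.5 | 60% vs 85% | 43% vs 72% | 27% vs 54% |

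At rho 0 with 40 pairs the figures are 58% vs 57%, so nothing is lost. Fewer than 40 pairs is plausible because of 5.1.2, step 5: "If LET-optimized IMPT plan is not deemed significantly superior, the conventional IMPT plan will be chosen". Patients treated on the conventional plan may not count as LET-optimized cases.

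**The case against.** **Severity.** Both endpoints are exploratory in a single-arm feasibility trial. No decision rule hangs on either p-value, and the plan for each patient is chosen by the physician. The paired data will exist, so an analyst could run the right test without any change in conduct. All of this is true and limits the severity, but the named test is still wrong.

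**Wording.** Recording dosimetric differences may be meant as within-patient differences. A rank-sum test cannot be run on one set of differences, so the sentence needs correction on that reading too.

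**Choice of shift.** The Endpoint 1 contrasts use a small shift. At 40 patients and rho 0.8, a 0.5 SD shift gives 68% vs 99.8%, and at 0.8 SD both tests are above 99%. The loss therefore disappears for large differences. Section 6.5.1 does not expect large ones.

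**Endpoint 2 is the weaker half.** Its pairs are different people, and nothing in the plan shows that T-stage, dose, age and gender induce correlation in nadirs. A paired test also drops incomplete pairs. With 40 controls, 8 study patients unavailable and a 0.5 SD shift, rank-sum vs signed-rank power is 52% vs 46% at rho 0, about 52% vs 51% at 0.1, 52% vs 56% at 0.2 and 53% vs 62% at 0.3. At low correlation the change can gain nothing, or cost a little. This stands, and the practical gain for Endpoint 2 is uncertain. The inconsistency with 7.4.1 remains.

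**Unseen control protocol.** Control data come under a separate protocol, so the matching ratio and the retention of pair identifiers cannot be confirmed here. McNemar's test in 7.4.1 already needs those identifiers.

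**Conclusion.** The concern holds. Both endpoints name a test for independent samples on data that the plan itself makes paired. For Endpoint 1 the loss is potentially severe, because shared anatomy and equalized coverage make high correlation plausible: 25 power points at rho 0.5 and 71 at rho 0.8 (40 patients, 0.3 SD). For Endpoint 2 with 40 pairs and 0.5 SD it runs from nothing at rho 0 to about 25 points at rho 0.5.

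These sizes rest on assumed correlations and shifts. The direction rests on positive correlation. At rho −0.3 the rank-sum type I error would rise to about 8.5%, and the paired test is the remedy there too. Overlarge p-values are a tendency across data sets, not a certainty in one. The primary comparison and the safety stopping rule are untouched. The correction should be made but is not critical.

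**What to change.** In 7.4.3:

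- **Endpoint 1.** Replace the rank-sum test with the Wilcoxon signed-rank test on within-patient plan differences. Report the Hodges-Lehmann difference with a 95% confidence interval for each dose measure. The current sentence covers only the two IMPT plans, so also state which patients supply the VMAT plans and how that arm of the comparison is analysed.
- **Endpoint 2.** State the matching ratio. If it is 1:1, use the signed-rank test on within-pair nadir differences, again with the Hodges-Lehmann estimate and interval. Otherwise use a stratified or mixed model with the matched set as the cluster. A mixed model also keeps incomplete sets, so if many are expected, choose it before the control data are seen.
- **Separate minor point.** Endpoint 2's objective is 12-week rates of leukopenia, neutropenia and lymphopenia, but its analysis is of on-treatment nadirs. The McNemar comparison of cumulative hematologic toxicity in 7.4.1 partly covers this. A cross-reference naming the three rates, where control values exist, would close the gap.

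The cost is two sentences on the tests, the short statements on VMAT plans and matching ratio, and one cross-reference. No new data are needed, provided pair identifiers are kept in the control data set. Pairs with a missing member drop out of the signed-rank test, and Endpoint 2 may have fewer than 40 pairs.
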